9.3 Treatment of Breakthrough Bleeding Episodes

Additional to version 2.0 of the SAP, all analyses described below will also be done for those bleedings reported during inhibitor-free periods.

The following will be presented following the manners of representation described in section 6:

- Number of BEs, rates of BEs (per site and type of BE)
 - Remark:* If the treatment of a BE in one bleeding site is interrupted for ≥ 48 hours, the event is to be recorded as two separate BEs; if however different Type of BE (spontaneous, traumatic, post-operative, other)
- Type of FVIII treatment (prophylactic, on-demand, ITI) at start of BE
- Site of bleeding episode
- Date and time of occurrence/of noticing and of end of the bleeding episode; the duration of the BEs will be calculated and presented as well
 - Treatment duration for BE =
End date/time – start date/time of BE;
if end time missing: impute 23:59 of same day,
if start time missing: impute 0:00 of same day.
- Severity of the BE (minor, moderate, major, life threatening) by type and by site of BE
- Efficacy assessment by the subject at the end of the bleeding episode, together with the investigator in case of on-site treatment (excellent, good, moderate, none)

In addition to the four point scale the proportion of BEs successfully treated with *Human-cl rhFVIII* will be evaluated for all BEs as well as for BEs of different severity. “Successfully treated” means all “excellent” and “good” efficacy ratings of treated BEs.

Subjects who permanently switch to another FVIII product during their study participation* will be considered treatment failures, i.e. the efficacy will be imputed to be “none” for each haemostatic efficacy assessment after the switch in the efficacy analyses.

There will be two exceptions for subjects switching to another FVIII product during their study participation which will **not** be considered treatment failures in the efficacy analyses:

- a) if the administration of another FVIII concentrate was due to an emergency situation (example: accident requiring treatment with FVIII without patient (or ICU personnel) having access to IMP product)
- b) if the IMP was not available for the patient in time (example: patient experiences severe BE but has not enough product available at home).

The efficacy assessment for a BE treated completely with a different FVIII due to one of these exceptions will not be evaluated for the efficacy of *Human-cl rhFVIII* (missing efficacy assessment).

In case the BE was treated partly with *Human-cl rhFVIII* and partly with another FVIII because of *one of the exceptions*, the efficacy of *Human-cl rhFVIII* in this BE cannot be rated and is set to missing assessment.

In case the BE was treated partly with *Human-cl rhFVIII* and partly with another FVIII because of *other reasons* than described in the exceptions, the efficacy of *Human-cl rhFVIII* in this BE cannot be rated better than “moderate”, i.e. if the investigator rated the efficacy as excellent, good or moderate the efficacy is set to “moderate”, if the investigator rated it as “poor” it remains “poor”.

* Subjects will be excluded from the PP population.

- Treatment details: number of exposure days, number of injections, dosing incl. batch nos., consumption of *Human-cl rhFVIII* (IU/kg BW per month, per year, per BE)
- Frequency of BEs
- Number of infusions needed to treat a BE
- Study drug consumption (FVIII IU/kg BW per infusion, per BE, per month, per year)
- Changes: increased and decreased doses of *Human-cl rhFVIII* (IU/kg BW) used to treat individual BEs.
For further definition of a dose change, see Chapter 3.4.2.
- Changes in the doses per infusion and changes in the total dose used to treat subsequent BEs of the same site (e.g. elbow, knee, etc.) in the same patient.
For further definition of a dose change, see Chapter 3.4.2.
- Any haemostatic co-medication will be listed.

9.4 **Haemostatic control in Surgical Procedures**

Additional to version 2.0 of the SAP all analyses described below will also be done for those surgical procedures performed during inhibitor-free periods.

The following will be presented following the manners of representation described in section 6:

- Number of subjects undergoing surgeries (minor, major, total)
- Number of surgeries (minor, major, total)
- Surgery characteristics (type and site, pre-planned or emergency, reason, severity, duration, average and maximal expected blood loss for the planned surgical procedure and for the same procedure in a subject with normal haemostasis and of the same sex, age, and stature, subject's body weight)
- Details on treatment for surgical prophylaxis (number of exposure days and injections prior to surgery, dosing details, total amount of *Human-cl rhFVIII*)

- Details on treatment with *Human-cl rhFVIII* during and post the surgical procedure (number of injections, dosing details amount of trial product)
- Characteristics and amount of other blood products or rescue medication administered at any time prior, during or post the surgical procedure
- Efficacy evaluation by the surgeon at the end of the surgery and by the surgeon and the haematologist on the last post-operative day (end of post-operative phase).

In addition to the four point scale (very good, good, moderate, none), the proportion of surgeries with successful treatment according to the overall efficacy assessment will be presented.

“Successfully treated” are all “excellent” and “good” efficacy ratings of surgical procedures.

Subjects who switch to another FVIII product during a surgery* will be considered treatment failures, i.e. the efficacy will be imputed to be “none” for each haemostatic efficacy assessment after the switch in the efficacy analyses for this surgery

* those surgeries will be excluded from the SURG-PP population.

- These patients may stay in the study until they have reached their regular end of the study
- Expected (average and maximum) and actual blood loss and difference between planned and actual blood loss
- Expected and actual duration of the surgical procedure and difference between expected and actual duration
- Pre-, intra-, and post-operative FVIII plasma levels
- Any wound haematomas and whether they require surgical evacuation
- Laboratory tests: haematology and clinical chemistry (pre- and postoperatively)
- Vital signs (pre- intra- and postoperatively)
- Details on concomitantly administered products including any blood/blood product transfusions but excluding drugs given for routine anaesthesia.

9.5 **On-demand treatment**

Study drug consumption data for on-demand treatment (IU FVIII /kg BW per month, per year; exposure days) per subject and in total (for subjects on prophylactic treatment) will be presented descriptively for subjects receiving on-demand treatment.

9.6 **ITI treatment**

The percentage of subjects under ITI treatment with complete success (inhibitor-free, normalised recovery and half-life; see Chapter 10) of the therapy will be displayed descriptively. Kaplan-Meier curves will show the distribution of the time to complete success.

Study drug consumption data for subjects with ITI treatment (IU FVIII /kg BW per month, per year; exposure days) per subject and in total will be presented descriptively.

9.7 **Resource Use Analysis Plan**

The statistical analysis of resource use parameters will be descriptive.

Continuous characteristics (i.e. drug usage, duration of hospitalisation, days lost at work, etc.) will be described in terms of mean/median/ standard deviation and range). Dichotomous or categorical variables (i.e. number of hospitalizations, CVAD use, etc.) will be described by frequency tables and percentages.

- Use of FVIII concentrates:
 - Prophylaxis or on-demand,
 - dose per kg body weight separated for prophylaxis and on-demand,
 - the frequency of injection separated for prophylaxis and on-demand,
 - duration of treatment separated for prophylaxis and on-demand,
 - any change in treatment regimen separated for prophylaxis and on-demand,
 - duration of FVIII treatment separated for prophylaxis and on-demand.
 - use of other haemostatic agents separated for prophylaxis and on-demand
 - number and time of hospitalizations (including ward type) separated for prophylaxis and on-demand
- Inhibitor status
 - any change in FVIII use when changing from negative to positive and vice versa,
 - use of other haemostatic agents separated for with and without inhibitor,
 - number and duration of hospitalization (including ward type) separated for with and without inhibitor.
- Bleeding episodes: location, severity and duration
Listings will indicate whether subjects were under prophylaxis, under on-demand or under ITI therapy and whether they had a positive inhibitor or not at the time of the BE.
- ITI: ITI regimen details (regimen type, FVIII use, dose per kg body weight, the frequency of injection, duration, other haemostatic agents, patients' inhibitor levels.
- CVAD (Central Venous Access Device):
 - CVAD type,
 - number and duration of hospitalizations (including ward type),
 - number and type of surgical procedures,
 - complications (adverse events) due to CVAD use and management of the complication (text variable), separated for with and without inhibitor.
- Surgery prophylaxis: dosage and duration of treatment with FVIII for surgery prophylaxis including details on the type of surgery
Listings will indicate whether or not the patient had a positive inhibitor at the time of the surgery.

Health economic modeling analysis with resource use parameters is planned at study closure; this part of the analysis is not objective of this analysis plan.

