    - Subjects by intensity of treatment with/without peak treatment moments before inhibitor appearance (peak treatment moments defined as ≥3 subsequent days with FVIII dosing)
    - Subjects by classes of prophylactic treatment (amount and frequency)
- Population of subjects on prophylactic treatment schedule (PROPH): All subjects in the ITT population who have at least one prophylactic treatment
- Per-protocol population of subjects on prophylactic treatment schedules (PROPH-PP): All subjects in the PP population who have at least 100 EDs of treatment and who have no significant dosing or treatment errors, like e.g. unexplained interruptions of the prophylaxis with *Human-cl rhFVIII*
- Population of bleedings (BLEED): All documented bleeds except those occurring during and after surgery of subjects in the ITT population for which
  - any amount of treatment with *Human-cl rhFVIII* is documented and which
  - start between first BE treated with *Human-cl rhFVIII* and the completion visit.
- Population of bleedings per protocol (BLEED-PP): All documented bleeds in the BLEED population of subjects in the PP population.
- Surgery population (SURG): All documented surgical interventions of subjects in the ITT population for which
  - any amount of *Human-cl rhFVIII* prior to, during or after the surgery is documented and
  - no other FVIII concentrate is documented within 24 hours prior to surgery.
- Surgery per-protocol population (SURG-PP): All documented surgical interventions of subjects in the PP population for which
  - any amount of *Human-cl rhFVIII* prior to, during or after the surgery is documented and
  - no other FVIII concentrate is documented within 72 hours prior to, during or after the surgery (until resuming regular prophylactic treatment or until discharge from hospital in case of a subject with on-demand treatment).

The subject disposition, i.e. the identification of significant violations to consider for the PP populations and the assignment of each subject, bleeding and surgery to these analysis populations, will be the joined decision of the trial statistician and the responsible medical expert prior to database lock.

Amended Study Protocol	CONFIDENTIAL	Version 05
No. GENA-05		01-Feb-2018

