- Population of subjects on continuous prophylaxis (PROPHcont): All subjects in the ITT population who have at least one prophylactic treatment and have been assigned to the subgroup of patients receiving continuous prophylaxis, i.e. prophylactic treatment period of at least 169 calendar days, and have not received a mixture of on-demand and prophylactic treatment (however, subjects who were treated on-demand only once and switched to prophylactic treatment thereafter, will be kept in this population).
- Population of subjects with on-demand treatment (OD): All subjects in the ITT population with at least one period of on-demand treatment. Only data under on-demand treatment will be used for the analyses.
(Definition of period under OD: A patient in the main study is defined to be under prophylaxis during all time periods within 14 days after each prophylactic treatment. A patient in the main study is defined to be under OD in time periods he is not under “Prophylaxis” according to previous definition)
- Population of BEs (BLEED): All documented treated BEs of subjects in the ITT population for which
 - any amount of treatment with *Human-cl rhFVIII* is documented (either the treatment is indicated with reason “Bleeding” or ITI treatment and an efficacy assessment for the BE is documented).
 - start between first BE treated with *Human-cl rhFVIII* and the completion visit*Note*: Any type of BE is included: spontaneous, traumatic, post-operative or other

Additional to version 2.0 of the SAP, part of the analysis will be restricted to BEs during inhibitor-free periods.

- Population of BEs per protocol (BLEED-PP): All documented bleeds in the BLEED population of subjects in the PP population, which
 - are *not* treated with another FVIII or bypassing agents

Note: Any type of BE is included: spontaneous, traumatic, post-operative or other

Additional to version 2.0 of the SAP, part of the analysis will be restricted to BEs during inhibitor-free periods.

- Surgery population (SURG): All documented surgical interventions of subjects in the ITT population for which
 - any amount of *Human-cl rhFVIII* prior to, during or after the surgery is documented and
 - no other FVIII concentrate is documented within 24 hours prior to surgery*.
- Surgery per-protocol population (SURG-PP): All documented surgical interventions of subjects in the PP population for which
 - any amount of *Human-cl rhFVIII* prior to, during or after the surgery is documented and

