6.4.2 Handling of Dropouts or Missing Data

In general, missing data values will not be imputed, except for the following:

- Body weight: In case of missing weight, the last available weight measurement will be used (last observation carried forward). Body weight will be estimated for the first exposure day: if body weight is not available on ED1 it will be estimated by linear interpolation between last available data before and after ED1.
- Date of birth: only month and year will be presented in listings.
- Age: calculations at screening and at ED1 in case of partially missing data:
 - If month and year available: “1” for day will be imputed
 - If month missing, but year available: “July” will be imputed
 - If month missing, but year available: “1st of July” will be imputed
 - no imputation otherwise
- Inhibitor measurement in the ITI study: In case inhibitor measurements have turned from positive to negative in the ITI sub-study and are missing at subsequent determinations of recovery and/or half-lives, they will be carried forward in order to facilitate the calculation of the number of ITI success criteria.
- Subjects who permanently switch to another FVIII product during their study participation, will be considered treatment failures, i.e. the efficacy will be imputed to be “none” for each haemostatic efficacy assessment after the switch in the efficacy analyses.

There will be two exceptions for subjects switching to another FVIII product during their study participation, and will thus **not** be considered treatment failures in the efficacy analyses:

- a) if the administration of another FVIII concentrate was due to an emergency situation,
- b) if the IMP was not available for the patient in time.

In either of these cases the efficacy will be considered a missing value with regard to *Human-cl rhFVIII*.

- Efficacy evaluation by the surgeon and the haematologist at the end of the surgery and on the last post-operative day (end of post-operative phase):
Subjects who switch to another FVIII product during a surgery will be considered treatment failures, i.e. the efficacy will be imputed to be “none” for all haemostatic efficacy assessment after the switch for this surgery. Exception: Not enough *Human-cl rhFVIII* study drug was available at the site; in this case the efficacy will be considered a missing value with regard to *Human-cl rhFVIII*.

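### The SAP rates bleeds after a permanent, non-exempt FVIII switch as 'none', but no bleed-efficacy table can contain those treated wholly with the other product

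*SAP*

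**What the plan says.** **The failure rule.** SAP 6.4.2 says: "Subjects who permanently switch to another FVIII product during their study participation, will be considered treatment failures". SAP 9.3 repeats this for bleeds and imputes 'none' "for each haemostatic efficacy assessment after the switch in the efficacy analyses". Both follow protocol 4.2.2. The two exceptions are emergency use and study drug not being available in time.

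**Bleeds treated wholly with another FVIII.** SAP 9.3 gives a rule only for exempt cases: "The efficacy assessment for a BE treated completely with a different FVIII due to one of these exceptions will not be evaluated". The rating is then missing.

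**Bleeds treated partly with each product.** Where no exception applies, SAP 9.3 says the efficacy of the study drug "in this BE cannot be rated better than" 'moderate'.

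**Populations.** BLEED requires, for each bleed, that "any amount of treatment with *Human-cl rhFVIII* is documented" (SAP 5.1). Protocol 9.2.1 sets the same condition: "any amount of treatment with *Human-cl rhFVIII* is documented and which". BLEED-PP is the part of BLEED that comes from PP subjects, and it also leaves out bleeds "treated with another FVIII or bypassing agents". A footnote in SAP 9.3 says of permanent switchers: "Subjects will be excluded from the PP population".

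**Outputs.** SAP section 13 assigns Tables 14.2.30.1 to 14.2.30.4 to BLEED and BLEED-PP only. SAP 5.1 names BLEED the most relevant set for bleed efficacy.

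**The concern.** The imputation rule and the table populations do not fit together. The rule covers every assessment after a permanent, non-exempt switch. The bleeds it most plainly describes, those managed entirely with the other product, meet neither population definition, so their 'none' has no table to enter.

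The four-point bleed rating is a secondary endpoint (SAP 3.4.2), and 9.3 derives a success proportion (excellent or good) from it. If such bleeds occur, that proportion omits failures that the SAP's text says are counted, and the omission can only favour the product. The study report could then describe a failure rule that its tables did not apply.

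A second, smaller conflict concerns bleeds treated partly with each product, where 'none' and the cap at 'moderate' both apply and no precedence is given.

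**Working it through.** The plan states no figure to reproduce. The check is a trace through the definitions, followed by arithmetic for scale.

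**1. Which bleeds can the rule reach?** Take a treated bleed that falls under the rule in a non-exempt permanent switcher.

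| Treatment of the bleed | In BLEED? | In BLEED-PP? | Rating under 6.4.2/9.3 | In Tables 14.2.30.1 to 14.2.30.4? |
|---|---|---|---|---|
| Other FVIII only | No (no study drug for the bleed) | No | none | No |
| Partly study drug, partly other FVIII | Yes, if the other BLEED conditions are met | No (subject is not in PP) | none, or moderate under the cap | Yes (BLEED) |

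The ITI alternative in the SAP's BLEED definition is also treatment with study drug, so it does not admit the first row.

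**2. Where does the first row appear?** Listing 16.2.6.3 covers bleeds inside and outside BLEED. Table 14.2.24.1 counts bleeds per subject in ITT. Neither summarises efficacy ratings. Listing 16.2.4.6.3, on co-medication used for bleeds, is itself limited to BLEED and BLEED-PP.

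**3. Effect on the success proportion.** Let B be the rated bleeds in BLEED, S the excellent or good ones, and p = S/B. Let k be the documented treated bleeds of non-exempt permanent switchers managed wholly with the other product.

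- Shown: S/B
- Under the SAP's failure rule: S/(B + k)
- Difference: S/B − S/(B + k) = p·k/(B + k) = p·r/(1 + r), with r = k/B

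The documents give no p, B or k, so the values below are assumptions.

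| r = k/B | p = 80% | p = 90% | p = 95% | Upper bound (p = 100%) |
|---|---|---|---|---|
| 0 | 0 | 0 | 0 | 0 |
| 1% | 0.79 | 0.89 | 0.94 | 0.01/1.01 = 0.99 points |
| 2% | 1.57 | 1.76 | 1.86 | 0.02/1.02 = 1.96 points |

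For a difference of at least t, k must be at least B·t/(p − t). With p = 90% and t = 1 point:

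- B = 100: 1/0.89 = 1.12, so k ≥ 2
- B = 500: 5/0.89 = 5.62, so k ≥ 6
- B = 1000: 10/0.89 = 11.24, so k ≥ 12

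**4. Partly treated bleeds.** The rating is made at the end of a bleed (protocol 7.2.2.2). A bleed in progress at the switch is therefore rated after it, and 'none' applies. The cap in 9.3 instead sets a rating of excellent, good or moderate to 'moderate'. Success means excellent or good, so the bleed is a non-success either way. Only the split between moderate and none changes.

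**5. Wording.** The cap in 9.3 refers to a rating of 'poor'. That belongs to the prophylaxis scale; the lowest bleed rating is 'none'.

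**The case against.** The strongest reply is that populations decide which bleeds are analysed and imputation rules decide values inside that set. BLEED's entry condition is printed in both documents and is itself a restriction. SAP 9.3 describes the quantity as bleeds successfully treated with the study drug, and a bleed that received none arguably lies outside it. For surgeries, SAP 5.1 says openly that only those performed under study drug are considered, which suggests the same principle. Section 9.3 also gives a missing-value rule for exempt bleeds treated wholly with another product, although these too are outside BLEED. Stating a rule there does not prove an intent to widen the denominator.

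Much of this stands. A reader might infer from the exception sentence that the SAP definitely means to score non-exempt bleeds as failures. That is a reasonable inference, but the documents do not say it. The mismatch remains on either reading: one section states a failure rule for every later assessment, and the populations keep part of those assessments out. The SAP explains its restriction for surgeries but does not reconcile the two provisions for bleeds.

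It can also be said that k will be small. Other FVIII products are forbidden, major deviations lead to a decision on continued participation (protocol 4.5), and the investigator may withdraw subjects (4.3.1). That is fair. But protocol 4.2.2 does not require withdrawal on switching, so k cannot be assumed to be zero.

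Finally, switchers remain visible through protocol deviations, PP exclusion and listings. This is true, and it means the bleeds can be found. It does not put them into the efficacy result.

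**Conclusion.** The point holds as a conflict between stated rules. The 'none' rule cannot act on post-switch bleeds treated wholly with the other product, so the success proportion is S/B where the SAP's own rule would give S/(B + k). The direction favours the product whenever k and S exceed zero.

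The size is unknown. The difference is below 1 point for any p if k is at most 1% of B, and it is zero if nobody makes a non-exempt permanent switch and then has such a bleed. Two stronger readings are not supported. One is that the reported success rate will be materially inflated; nothing in the documents supports a large k relative to B. The other is that the clash between 'none' and 'moderate' distorts the success proportion; it cannot.

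The analysis is descriptive, has no stated success threshold, and leaves the primary immunogenicity endpoint untouched. If exclusion is intended, S/B is the right figure and only the rule's description needs changing. The trace is firm; the intended handling is inferred. Priority is low to moderate.

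**What to change.** Keep BLEED as the main set, and do one of the following.

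1. **Apply the rule once.** Add one sensitivity display to Tables 14.2.30.1 to 14.2.30.4. It should cover BLEED plus treated bleeds that start after a permanent, non-exempt switch, up to completion or withdrawal, with those bleeds rated 'none'. Report the number of permanent switchers and the number of such bleeds, including zero.
2. **Or state the exclusion.** Say in SAP 6.4.2 and 9.3 that the 'none' rule applies only to bleeds in BLEED, and still report the two counts.

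In either case, state whether 'none' or the cap at 'moderate' takes precedence for a non-exempt bleed treated partly with each product at or after a permanent switch. Replace 'poor' with 'none' in 9.3.

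**Cost.** Option 1 needs SAP wording, one population flag and one display, from bleeds already recorded under protocol 7.2.2.2 and listed in 16.2.6.3. The sensitivity figure may be slightly less favourable than the main one. Option 2 needs wording and two counts. Neither captures later bleeds of patients who leave the study at the switch, so only the switcher count shows them.
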